1.1 Synopsis

Title: Comparing teaching before vs after simulation education on pediatric status epileptics: A randomized controlled trial

Study Description: The study will test whether simulation preceding didactic teaching leads to improved knowledge and performance retention compared to a didactic lecture preceding simulation. Participants will be randomized to one of two different groups: 1) didactic teaching followed by simulation or 2) simulation then didactic teaching.

Primary Outcomes:

1. Resuscitation performance retention score 3 months post-initial training

Secondary Outcomes:

2. Knowledge assessment 3 months post-initial training
3. Learner satisfaction

Hypothesis:

1. Didactic teaching after simulation-based training will be more effective in maintaining retention of knowledge and skills in the management of pediatric status epilepticus compared to didactic teaching prior to simulation

Study Population: Second year medical students from the University of British Columbia – Vancouver Campus

Description of Sites: The intervention will take place at BC Children’s Hospital Simulation Centre with trained facilitators and high-realism simulation equipment.

Description of Study Intervention: One arm of the study will receive a 60-minute lecture on pediatric status epilepticus management and then complete a simulation scenario immediately after. The second arm will complete a simulation scenario on pediatric status epilepticus without knowing the topic beforehand and will complete a 60-minute lecture immediately after the simulation session. Both groups will complete a knowledge test directly after the intervention. Both groups will be reassessed in three months with a repeat simulation scenario on pediatric status epilepticus and repeat knowledge test.

Study Duration The study will enroll participants for 2 months and then complete the educational intervention over 3 months.

Participant Duration: The participants will participate in one 60-minute lecture and two ten-minute simulation sessions and one focused 15 minute debrief over the course of four months’ time.

1.2 Schema:

[figure not shown]

Figure 1: Flow of participants through the research project

2 Introduction

2.1 Background Information & Rationale

Simulation is a revolutionary tool in medical education and specifically pediatrics with the rarity of life-threatening situations. It provides learners with the opportunity to practice high-stress crucial medical scenarios in a safe and supportive environment where mistakes are instead valuable teaching for future experiences. Simulation has been shown to be an effective teaching method in medical education however how best to optimize retention and patient outcomes remains unclear¹⁻³. Medical education interventions are typically evaluated at one stage of Kirkpatrick's framework for learning which include reaction (level 1), learning (level 2), behavior (level 3) and results (Level 4)⁴. Patient outcomes remains the strongest measure however is difficulty to effectively design projects to show this^{5,6}. In pediatrics procedures and adult ACLS retention of knowledge and skills have been shown to decline by as early as 3-months' time in two systematic reviews^{7,8}. In our assessment, it remains unclear what the best method of teaching associated with simulation is and when the best time to facilitate this teaching to improve retention for medical expert knowledge and resuscitation performance.

Pre-simulation assignments may be an effective way to prime participants for learning in simulation. Different methods including reading, written assignments, plan of care mapping, pre-quizzes, scenario demonstration, virtual reality, lectures and online games have been described⁹⁻¹⁶. No method has been identified as superior^{17,18}. Pre-simulation preparation was felt to improved learning in one systematic review however the strength of the evidence was weak and primarily level 1 and 2 outcomes were assessed^{17,19}. There remains contention in the literature with one study finding adding simulation to a flipped classroom teaching model improving 3-month retention though multiple studies examining a flipped classroom model in rapid-cycle deliberate practice models found no improvement^{11,20,21}. New evidence suggests there may be better immediate knowledge gain from simulation preceding didactic teaching compared to didactic teaching before simulation^{22,23}. For procedural skills it has been shown the practical sessions before theory-based lectures resulted in increased skill and knowledge retention at one month for transesophageal echocardiography²⁴.

Pediatric seizure is a common acute care pediatric scenario with numerous published simulation scenarios²⁵⁻²⁷ and evaluation rubrics available as well as multiple high-quality national pediatric status epilepticus management algorithms available^{28,29}. The effect of pre and post simulation teaching remains debated in medical education literature as well as the ongoing concern of knowledge and performance degradation. This study aims to investigate the effect of pre and post teaching on knowledge degradation, and how to best optimize knowledge retention to improve medical education and theorized patient care. The specific objectives are to assess whether teaching before or after a simulation leads to medical students' improved knowledge and resuscitation performance retention at two to fourth months post educational intervention for managing pediatric status epilepticus.

2.2 Risk/Benefit Assessment

2.2.1 Known Potential Risks

As this is a medical education study there are minimal risks to the participants. The participation in simulation could cause increased stress to the learner but this will be minimized with structured pre-brief and debrief sessions.

2.2.2 Known Potential Benefits

The participants will benefit from two simulation teaching sessions with a trained simulation expert and FRPC certified pediatric emergency medicine physician. They will also receive an additional lecture providing them with didactic teaching on status epilepticus.

3 Objectives

The primary objective is to assess the resuscitation performance retention difference between the two educational intervention arms at two to four months following teaching.

The secondary objectives are to assess the difference in knowledge between both study groups immediately after and two to four months after the educational intervention. In addition, we will measure the comfort of learners performing the initial simulation scenario.

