3.1 Outcome Measures

The primary outcome will be the resuscitation performance retention assessed using the post-teaching the final global rating scale score (1-7 performance score) for medical management and flow during each simulation as well as the following “time-to” metrics; glucose check, IV access, chemistry panel order, first-line anti-epileptic administration³⁰, second line anti-epileptic administration. This will be adjusted for baseline score.

The secondary outcome measures for knowledge retention assessment will be the post-teaching knowledge test score assessed on a 15 Question MCQ test administered at the final assessment adjusted for the baseline score.

Comfort/Confidence will be assessed using the change in Likert scale item after each simulation and debrief.

4 Study Population

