4.2 Expected Duration of Subject Participation

A participant will already be expected to attend a 60 min teaching session on status epilepticus. They will also be required to participate in two 10-25 min simulation sessions which will include a 10-minute simulation and 15 debrief for the first and only a 10-minute simulation the second time.

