The LS group will complete the 60-minute focused lecture immediately prior to their initial simulation. The SL group will complete the 60-minute focused lecture immediately after their initial simulation. The LS group will complete a pre-intervention knowledge test prior to the lecture and the SL group will complete a knowledge test prior to the initial simulation.

Both groups will complete the initial simulation in groups of 3-4 with one member acting as the leader and others acting as team members. The simulation will last for 10 minutes followed by a structure debrief using the +/-delta method lasting up to 20 minutes. The debrief will be completed by a pediatric emergency medicine specialist with experience in leading simulation debrief. The leader of the group will be recorded for later subgroup analysis.

Every individual will complete a second evaluatory simulation 3 months after the initial simulation to evaluate the primary outcome of resuscitation performance retention. Each participant will act as the simulation leader with two actors who will function as a highly trained nurse and second physician but will not provide advice. The simulation will be videotaped. The participants will also complete a knowledge test prior after the second simulation.

Simulation videos will be reviewed as per the above data collection method to determine outcome measures. The simulations will be completed in the BCCH simulation center with a trained pediatric simulation expert and simulation facilitator. A high-fidelity mannequin will be used. It can seize and has appreciable chest rise and breath sounds. The participants will be instructed to assume all medications requested are drawn up in a syringe to the dose desired in the medication tray to decrease variability in time to metrics from difficulty in drawing up medications.

6 Statistical Consideration

6.1 Sample Size Determination:

The one paper assessing knowledge and skill retention comparing SL and LS structured teaching found a 13.42% difference in skill performance on transesophageal echocardiography²⁴ with the following means and std; LS group 71.90 (18.59) and SL group 85.32(15.63). Using a sample size calculator estimates a sample size of 60 with an alpha of 0.05 and power of 0.8³¹.

6.2 Statistical Analysis:

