The recorded simulation sessions will be reviewed by two separate pediatric emergency medicine and simulation experts who will evaluate the participants on the simulation global rating scale, a validated assessment tool for simulation. Inter-rater reliability will be calculated via Pearson correlation and ICC statistics, and the final reported value will be the mean of both reviewers.

The recorded sessions will also be reviewed to the time to metrics by two reviewers with a masked co-investigator serving as the tie breaker in times of significant discordance. Time zero for the “time to” metrics will be when the facilitator finishes the scenario description.

The mean and 95% confidence interval of the metrics will be calculated for each group. Post randomization scores will be compared using a paired t-test, and with mixed effects linear models using pre-randomization score as a covariate. Time-to-event measures will be displayed with Kaplan Meier graphs and median time, and tested with the log-rank test, and secondarily using Cox proportional hazards models. Regression models may include adjustment for baseline variables imbalanced between arms or prognostic of outcome. Secondary Likert outcomes will be assessed with a proportional odds model. All results will be presented with appropriate 95% confidence intervals. Statistical analysis will be completed with statistician support using R statistical software.

Protocol Deviations:

All deviations will be reported to the REB in a timely manner.

7 Data Handling and Record Keeping:

7.1 Data Management Responsibilities:

The data will be stored on a secure redcap data-server. The server will be password protected and only the research team will have access to the data. Participant data will only be stored de-identified. The video recordings will be stored on an encrypted external hard drive kept in the PI's office locked office in a locked drawer. The original video data would be deleted from the simulation center.

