31. Kane S. Sample Size Calculator. ClinCalc.com. Published July 24, 2019. Accessed October 17, 2022. <https://clincalc.com/stats/samplesize.aspx>

**Appendix A:
Demographics:**

Please enter your age:

What is your experience with medical simulation?

a) No experience b) 1-5 simulation experiences c) 5-10 simulation experiences d) >10 simulation experiences

Before entering medicine please check any roles that apply?

- Background in ED Nursing
- Background as a paramedic or first responder?

Confidence Quiz:

Please rate your anxiety in the simulation experience from 1 to 5?

1 – Extremely anxious 5 – Not anxious at all

Please rate your confidence in managing pediatric seizures in the future?

1 – Not confident at all, 5 – extremely confident

Please rate your satisfaction with the educational experience (Simulation + Debrief + Lecture)?

1 – extremely dissatisfied , 5 extremely satisfied

Initial priorities

- Cardiorespiratory monitor, BP and temp
- Point of care glucose
- 100% oxygen via non-rebreather mask
- IV access
- Tylenol
- Primary survey
- Initial anti-seizure medication

Powered by **Dall E Everywhere**

Stabilization

Initial Management

- Initiate ABCs, cardiorespiratory and BP monitoring
- O₂ 10-15 L/min via non-rebreather mask
- Prioritize giving the first dose of benzodiazepine as early as possible, followed by checking blood glucose
- Monitor for respiratory depression, hypotension, arrhythmias
- Give acetaminophen 15 mg/kg/dose (MAX 650 mg) PR if febrile
- Consider other investigations:**
 - Electrolytes, blood gas, calcium, CBC, serum glucose
 - Other: anticonvulsant drug levels, LFTs, blood & urine culture

Primary Survey – A - Airway

Recognize	Assess for	Manage
A Airway Obstruction	
 Position (hyper/hypo extension) Patency (Blood, Vomiting) Need for protection 	
 Oral Suction Sniffing Position Oral Airway Jaw thrust Bag-mask ventilation

Primary Survey – B - Breathing

Recognize	Assess for	Manage

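### The comfort objective concerns the initial simulation, but section 3.1 derives comfort as a change score, which does not estimate it

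*Combined protocol and SAP*

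**What the plan says.** Section 3 (Objectives) closes its secondary objectives with: "In addition, we will measure the comfort of learners performing the initial simulation scenario". This is a level on one occasion.

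Section 3.1 gives the only derivation: "Comfort/Confidence will be assessed using the change in Likert scale item after each simulation and debrief". It does not say which item is meant, which ratings are compared, or which is subtracted from which.

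Appendix A, under the Confidence Quiz, has an anxiety item, "Please rate your anxiety in the simulation experience from 1 to 5", anchored "1 – Extremely anxious 5 – Not anxious at all". A confidence item about managing future seizures is anchored "1 – Not confident at all, 5 – extremely confident". A third item asks about satisfaction with the simulation, debrief and lecture taken together.

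Section 6.2 says: "Secondary Likert outcomes will be assessed with a proportional odds model". It does not say whether the response is a single rating or a change. The synopsis lists learner satisfaction, not comfort, as the second secondary outcome.

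**The concern.** The objective asks for a level and the outcome measure supplies a difference. With a true pre-randomisation baseline this would be a familiar choice of scale. Here the first rating comes after allocation has acted: section 5.4 says "The LS group will complete the 60-minute focused lecture immediately prior to their initial simulation", while the SL arm meets the scenario first and hears the lecture afterwards. A difference between arms in that rating is the result the objective seems to be after. Subtracting the rating, or adjusting the final rating for it, removes that result.

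At stake is a stated secondary objective that the analysis would leave unanswered. In some circumstances the reported comfort result would also favour the arm that was less at ease in the first simulation.

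**Working it through.** The documents give no effect size, variance or power for comfort, so there is no planned figure to reproduce. The total of 60 in section 6.1 rests on skill performance. It is used here only to set 30 per arm, assuming equal allocation.

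**Step 1. Inputs from the documents.**
- Objective: one occasion, the initial simulation (section 3).
- Derivation: a change, with item, time points and order left open (section 3.1).
- Scales: 1 to 5, higher is better on both the anxiety and the confidence item (Appendix A).
- Lecture order: before the first simulation in LS, after it in SL (section 5.4).
- Debrief: section 4.2 describes a "10-minute simulation and 15 debrief for the first and only a 10-minute simulation the second time".
- Teams: the first simulation is run in groups of 3 to 4, the second with each participant leading alone (section 5.4).

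**Step 2. What each reading of change estimates.** Let D1 be the difference between arms (A minus B) in the rating after the first simulation, and D2 the same after the second. The objective corresponds to D1.
- Second minus first: D2 - D1. The initial rating has weight -1.
- First minus second: D1 - D2. The sign of D1 is right, but it is mixed with comfort about three months later.
- Before versus after a simulation: no pre-simulation rating is described, and the anxiety item asks about the simulation just experienced. The confidence item could be asked beforehand, but no such administration is planned.
- Literally after each simulation and debrief: on section 4.2 only the first session has a debrief, which leaves one rating and no change.

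No reading returns D1. The first is the workable one, although the text does not state it.

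**Step 3. Arithmetic for second minus first, with an assumed D1 of 1.0 point.**
- D2 = 0: 0 - 1.0 = -1.0
- D2 = 0.5: 0.5 - 1.0 = -0.5
- D2 = 1.0: 1.0 - 1.0 = 0
- D2 = 1.25: 1.25 - 1.0 = +0.25

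The initial rating analysed on its own gives +1.0 in all four cases.

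**Step 4. Simulation through the proportional odds model.** Assumed: 30 per arm, latent initial lead 1.0 for arm A, between-person and residual SD 0.7 each, values rounded to 1-5, independent participants, 200 runs per row.

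| Latent final lead of A | Median log OR, change | Significant against A | Significant for A | Median log OR, initial rating | Significant for A, initial rating |
|---|---|---|---|---|---|
| 0 | -1.74 | 94.5% | 0% | +1.68 | 92% |
| 0.5 | -0.85 | 38.5% | 0% | +1.80 | 96% |
| 1.0 | -0.05 | 2% | 3.5% | +1.76 | 94.5% |
| 1.5 | +0.71 | 0.5% | 32% | +1.71 | 92.5% |

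Smaller assumed leads (0.5 to 0.8 SD, within-person correlation 0.3 to 0.5, 30 per arm, 250 runs) with no final difference gave change scores significantly against the initially more comfortable arm in 30% to 44% of runs at 0.5 SD and 66% to 76% at 0.8 SD. Those percentages depend on setting the final difference to zero.

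**Step 5. Shared sessions.** Initial ratings come from teams of m = 3 to 4, so the variance of an arm mean is inflated by 1 + (m - 1)ρ, that is 1 + 2ρ to 1 + 3ρ. The documents give no ρ. Step 4 takes ρ = 0, so its significance percentages are only illustrative.

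**The case against.** The strongest reply has four parts.

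- **The objective may be descriptive.** For knowledge, section 3 speaks of a difference between groups; for comfort it says only that it will be measured. A rating collected after each simulation would include the first one, so reporting it could meet a purely descriptive aim. This is fair as far as the wording goes. But section 3.1 names only the change as the outcome, so the plan as written does not commit to reporting the initial rating at all.
- **The item and the subtraction order are inferred.** This stands. Nothing ties comfort to the anxiety item, and section 3.1 joins comfort and confidence. The inference is reasonable because only the anxiety item asks about the simulation itself. The open order does not rescue the derivation, since Step 2 shows that neither order gives D1.
- **The reversal depends on what happens by the second rating.** This also stands. A reader might infer that the arm more comfortable at first must score worse, or that the trial will report the opposite of the truth. The documents do not support either. The sign turns only if the initial lead shrinks; a lead kept in full gives zero, and one that grows keeps its sign. Nothing in the documents says the arms will be equal at three months. A larger improvement in one arm also answers a different question; it does not claim that this arm was more comfortable initially.
- **The mismatch could be settled the other way,** by rewriting the objective to ask about change. That is open to the sponsor, but it gives up the stated aim and would need time points and direction that section 3.1 lacks.

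**Conclusion.** The point holds as a mismatch between objective and outcome measure. Section 3 asks about comfort in the initial simulation; section 3.1 derives a change; and the first rating is post-randomisation and open to influence by allocation. No reading of the change estimates the stated quantity. On second minus first, the initial rating carries weight -1: a lead that fades counts against the arm that had it, and a lead fully kept disappears from the result.

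The algebra needs no assumption beyond that subtraction order. Any size does. With an assumed lead of 1.0 point, the change difference runs from -1.0 to +0.25 over the cases in Step 3. The frequency of a significant result in the wrong direction runs from 94.5% to 0.5% over the final leads simulated in Step 4, treating team members as independent. These figures show dependence on unknowns and are not a forecast for this trial.

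The outcome is secondary and the primary analysis is untouched, but the wording should be settled before analysis.

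**What to change.** In section 3.1, define comfort as the Appendix A anxiety rating (1-5, higher meaning less anxious) given after the initial simulation and debrief, and before the lecture in the SL arm. Compare it between arms with the planned proportional odds model, allowing for the shared initial team session, for example with a random team effect or team-clustered standard errors.

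Report confidence as its own outcome. If a change is also wanted, list it separately with its two time points and its direction, and do not present it as the answer to the comfort objective. Then bring section 3, section 3.1, section 6.2 and the synopsis, which names learner satisfaction, into agreement.

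The timing needs to be explicit. The quiz also asks for satisfaction with the lecture, so SL students may otherwise complete the whole form after it. If the form is now planned as one sitting at the end of the session, the anxiety item would have to be asked earlier in that arm.

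The item exists, the model is planned, and the sample size does not change. The cost is protocol wording and one more separately reported secondary Likert outcome.

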3.1 Outcome Measures

The primary outcome will be the resuscitation performance retention assessed using the post-teaching the final global rating scale score (1-7 performance score) for medical management and flow during each simulation as well as the following “time-to” metrics; glucose check, IV access, chemistry panel order, first-line anti-epileptic administration³⁰, second line anti-epileptic administration. This will be adjusted for baseline score.

The secondary outcome measures for knowledge retention assessment will be the post-teaching knowledge test score assessed on a 15 Question MCQ test administered at the final assessment adjusted for the baseline score.

Comfort/Confidence will be assessed using the change in Likert scale item after each simulation and debrief.

4 Study Population

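### Section 3.1 makes six measures primary and no section says which one decides the trial, while the sample size covers a single comparison of two means

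*Combined protocol and SAP*

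**What the plan says.** Section 3.1 (Outcome Measures) sets the primary outcome as the "final global rating scale score (1-7 performance score) for medical management and flow during each simulation as well as the following" five times: to glucose check, to intravenous access, to ordering chemistry, and to the first- and second-line anti-epileptic drugs. It then adds: "This will be adjusted for baseline score". It does not say which score serves as baseline.

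Section 1.1 (Synopsis) lists one primary item: "Resuscitation performance retention score 3 months post-initial training". It names no instrument and gives no formula for combining measures. Section 5.4 (Study Protocol) describes the assessment: "Every individual will complete a second evaluatory simulation 3 months after the initial simulation to evaluate the primary outcome of resuscitation performance retention".

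Section 6.1 gives 60 participants at alpha 0.05 and power 0.8. The basis is one published difference in a percentage skill score: 71.90 (SD 18.59) in the lecture-first (LS) arm against 85.32 (SD 15.63) in the simulation-first (SL) arm.

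Section 6.2 gives one set of methods for scores: "Post randomization scores will be compared using a paired t-test, and with mixed effects linear models using pre-randomization score as a covariate". It gives another for times, which are "tested with the log-rank test, and secondarily using Cox proportional hazards models". Neither section names a deciding measure, a composite, a testing order, a division of alpha, or a rule on whether one win is enough or all six are needed.

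**The concern.** The rule for a positive trial is missing, and the possible rules have different error rates and power.

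- **The GRS decides, or is tested first.** Alpha stays at 0.05 and the sample size in 6.1 has a matching test.
- **Any one of the six is enough, each at 0.05.** Six chances of a false-positive result replace one.
- **All six must succeed.** Alpha is held, but power cannot exceed that of the weakest single measure.

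Without a stated rule, a mixed result has no agreed meaning. A faster first drug with no difference in GRS could be reported as a primary success or as a primary failure. If the choice is made after the results are known, 0.05 no longer describes the error rate of the claim.

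**Working it through.** **1. Reproduce the plan's N.** The inputs from 6.1 are a difference of 85.32 − 71.90 = 13.42, SDs of 18.59 and 15.63, alpha 0.05 and power 0.8. Two-sided testing, 1:1 allocation and no dropout are assumptions, because the documents state none of them.

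n per arm = 2 × SD² × (z₀.₉₇₅ + z₀.₈₀)² / difference², with (1.960 + 0.842)² ≈ 7.849.

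- SD 18.59 in both arms: 2 × 18.59² × 7.849 / 13.42² = 30.1 per arm. This is 60 in total by nearest rounding, or 62 rounding up. Power at 30 per arm is 0.798 (normal approximation).
- Both SDs (root mean square 17.17): 25.7 per arm, 52 in total.
- SD 15.63 in both arms: 21.3 per arm, 44 in total rounding up.
- One-sided, SD 18.59: 23.7 per arm, 48 in total.

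The stated 60 is matched by one two-sided comparison of two means using the LS arm's SD, with no allowance for further primary tests.

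**2. Count the primary measures.** One GRS plus five times makes six.

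**3. False-positive chance if any one win counts.** Take six standard normal test statistics with common correlation r, no true difference on any, and critical value 1.96. If they are independent, the chance is 1 − 0.95⁶ = 0.265. Otherwise,

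P(at least one |Z| > 1.96) = 1 − ∫ [Φ((1.96 − √r·x)/√(1−r)) − Φ((−1.96 − √r·x)/√(1−r))]⁶ φ(x) dx.

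| r (assumed) | 0 | 0.3 | 0.5 | 0.7 | 0.8 | 0.9 |
|---|---|---|---|---|---|---|
| P(at least one) | 0.265 | 0.241 | 0.207 | 0.164 | 0.139 | 0.108 |

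Simulation with 400,000 draws at each r from 0.3 to 0.9 agrees to within 0.001.

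**4. Power under the other rules at 30 per arm.** As an illustration only, give every measure the planned standardised difference of 13.42 / 18.59 = 0.72. The documents supply no effect for the times.

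- Bonferroni, 0.05 / 6 = 0.00833: power for any one named measure is 0.56, and 94 in total would be needed for 0.80. The chance of at least one win is 0.99, 0.95, 0.90, 0.83 and 0.72 at r = 0, 0.3, 0.5, 0.7 and 0.9.
- All six required: 0.26 if independent, rising from 0.39 to 0.67 as r goes from 0.3 to 0.9.

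**5. A time deciding alone.** The Schoenfeld formula gives the hazard ratio detectable with 80% power as exp[(1.960 + 0.842) / √(events/4)]. With events in all 60 participants it is about 2.06; with 36 events it is about 2.54. Section 6.1 gives no hazard ratio or event count, so its power of 0.8 was not derived for a log-rank test.

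**The case against.** The best case for the plan is that it already points to one measure. The synopsis has a single primary item called a score, 6.1 sizes one difference in means, and no section says that one win out of six is enough. On a GRS-led reading the error rate is 5%. This stands to the extent that the inflation is conditional on a rule the plan does not adopt. It does not supply the missing rule: the synopsis names no instrument, the sample size borrows a different skill score, and 3.1, the section that defines outcomes, joins the times to the GRS on equal terms. The one ranking in 6.2, log-rank before Cox, orders methods and not outcomes.

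Equal correlation is also a rough model. In both Appendix C scenarios intravenous access becomes obtainable only after a first intranasal dose, and the named second-line agent is intravenous. Those three times are therefore partly sequential, while glucose check and chemistry order are not tied in this way. This stands, and it is why only a range is given. Even at 0.9 throughout, the chance is about twice the nominal 5%.

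The match to 60 depends on using the larger SD and rounding 30.1 down. That is fair, and the match is used only to show that one comparison was sized.

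A reader might infer that alpha 0.05 and power 0.8 can hold together only if one continuous measure decides or goes first. That is too strong. A pre-specified composite would serve. An all-six rule holds alpha. Bonferroni with any-of-six success holds alpha and can exceed 0.8 for at least one win if several measures truly differ. None of these is specified, and the last depends on effects and correlations that the documents do not give.

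Finally, the choice of hierarchy belongs to the investigators. That is true; what is essential is that a rule is stated. The GRS is proposed because a score analysed by comparing means is what the sample size assumes.

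**Conclusion.** The concern holds: six measures share primary status, they are tested separately without multiplicity control, and the trial is sized for one comparison of two means. If any one win counted, the false-positive chance would be about 11% to 26%, depending on correlations that are assumed. If the GRS alone decides or is tested first, it is 5%.

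Two further inferences would go too far. The documents do not show that the sponsor intends to claim success on any single measure; they leave the matter open. Nor do they show that 60 is too few on this account: with one deciding score, the stated basis still applies. That power does assume that a difference of 0.72 SD carries over from an echocardiography skill score to the 1–7 GRS, which the documents do not establish.

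Because the missing rule determines what counts as a positive trial, it should be settled before analysis.

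**What to change.** Before analysis, state the same rule in 1.1, 3.1, 6.1 and 6.2:

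- The GRS at the final individual simulation, averaged over the two raters, is the sole primary outcome. Alternatively, it is the first step of a fixed sequence in which the order of the five times is written down.
- It is tested two-sided at 0.05 by one named between-arm comparison of independent groups, for example the arm term in a linear model of the final GRS. The arms contain different people, so a paired test does not make this comparison.
- The five times are secondary, or later in the sequence. They are reported with 95% confidence intervals and cannot by themselves support a positive primary conclusion.
- The assessment window is worded the same throughout. Sections 1.1 and 5.4 say 3 months; sections 2.1 and 3 say two to four months.

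A linked but separate point concerns the covariate. Any baseline term in the primary model should be measured before the intervention. The initial simulation does not qualify in the LS arm: "The LS group will complete the 60-minute focused lecture immediately prior to their initial simulation". The knowledge test does: "The LS group will complete a pre-intervention knowledge test prior to the lecture", and section 5.4 has the SL arm take one before its initial simulation. The references to a baseline score in 3.1 and a pre-randomization score in 6.2 should be reworded to match.

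The cost is wording only, with no change to N, visits or data collection. The downside is that a favourable time metric alone can no longer be claimed as a positive primary result.
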